3.1.1 Definition of clinically significant toxicity

1. Grade 4 hematological toxicity or Grade ≥ 3 thrombocytopenia with hemorrhage, Grade ≥ 3 neutropenia with fever and infection;
2. Grade ≥ 3 non-hematological toxicity (except for abnormal laboratory test parameters), hypertension, rash, diarrhea, nausea, and vomiting that cannot be controlled after symptomatic treatment;
3. Grade ≥ 3 abnormal laboratory test parameters that lead to medical intervention, hospitalization, or lasting for ≥ 7 days;
4. SHR-1210 interruption for > 14 days due to relevant toxicity (delayed administration in Cycle 1 or Cycle 2);
5. Apatinib interruption for > 7 days due to relevant toxicity.

3.1.2 Definition of subjects with incomplete tolerance evaluation:

During the observation period of tolerability, the dose of SHR-1210 is < 90% of the prescribed dose due to non-clinically significant toxicity (such as injection reactions).

Subjects who do not complete the tolerability evaluation will not be included in the overall number of subjects undergoing tolerability evaluations, and each dose group is required to have ≥ 10 subjects for the tolerability observation.

Exemption: If ≥ 7 subjects in a dose group do not develop clinically significant toxicity during the tolerability observation period, the dose group is considered to be tolerable and no new subjects will be enrolled into this dose group.

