3 STUDY DESIGN

3.1 Overview of Study Design

Study design of Stage I:

A multi-arm, multi-center, open-label clinical study.

Inclusion criteria: Patients with advanced NSCLC who have failed standard treatment.

Three dose groups, i.e., 250 mg apatinib, oral, q.d. + 200 mg SHR-1210, IV, q2W, 375 mg apatinib, oral, q.d. + 200 mg SHR-1210, IV, q2W, and 500 mg apatinib, oral, q.d. + 200 mg SHR-1210, IV, q2W are set up. Ten to twelve subjects will be enrolled in each dose group (to make sure that at least 10 subjects will complete the tolerability evaluation), and the first cycle (28 days) of continuous treatment will be used as the observation period for tolerability. A dose will be considered tolerable if the proportion of subjects with clinically significant toxicity is < 0.33 .

Tolerability observation will be performed sequentially from the low dose group to the high dose group, and the tolerability observation of a latter dose group can only be carried out after the previous dose group is confirmed to be tolerable.

The first 3 subjects in each dose group will be enrolled on a case-by-case basis with an interval of not less than 14 days, and subsequent subjects can be enrolled at the same time.

After completing the tolerability observation period, subjects will continue the treatment until occurrence of any event that meets the criteria for discontinuation.

After the completion of the tolerability observation in Stage I, the study will enter Stage II for further observation of efficacy and safety.

In addition, after a certain dose group completes the tolerability observation in Stage I and is confirmed as tolerable, 10 to 12 subjects will be enrolled into this dose group for an expanded pharmacokinetic study. In cycle 1 of the expanded PK study, one dose of SHR-1210 will be administered on D1 followed by PK blood sampling. Then, apatinib will be started on D22 after the completion of PK blood sampling, while another PK blood sampling will be carried out on D28. Starting from D1 in cycle 2, SHR-1210 will be administered once every 14 days, while apatinib will be administered orally every day. PK blood sampling will be carried out on D1 of cycle 2 after the administration of SHR-1210 and on D28 after the administration of apatinib. After the blood sampling is completed, the subjects will continue to receive the study treatment until an event meeting the criteria of study termination occurs.

Design of Stage II Study:

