5.1. General Considerations

5.1.1. Analysis sets

Full analysis set (FAS)

All enrolled subjects who have received at least one dose of the study drug are included.

Evaluable analysis set (ES)

ES is a subset of FAS, which is defined as the subjects who have received at least one dose of the study drug, and have at least one post-baseline imaging response evaluation. If there is a new anti-tumor treatment, there should be a post-baseline tumor imaging response evaluation no later than the start date of the new anti-tumor treatment.

Per-protocol set (PPS)

All enrolled subjects who have received at least one dose of the study drug without major protocol deviation.

Safety set (SS)

All enrolled subjects who have received at least one dose of the study drug.

DLT analysis set

Subjects enrolled in Stage I who have developed DLT during the tolerability observation period (four weeks) or have completed the tolerability observation period. Subjects with SHR-1210 dose < 90% of the prescribed dose due to non-clinically significant toxicity (such as injection reaction) during the tolerability observation period are not included in the DLT analysis set.

Table 1. Analysis sets and corresponding endpoints

Endpoint	Analysis Sets				
	FAS	ES	PPS	SS	DLT Analysis Set
BOR (%)	X	X	X		
ORR (%)	X	X	X		
CBR (%)	X	X	X		
TTR (months)	X				
PFS (months)	X				
DoR (months)	X				
12-Month Overall Survival Rate (%)	X				
OS (months)	X				
Safety (AE, LAB, VS, ECG, and PE)				X	
DLT Events					X

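### The Stage I tolerability denominator has no apatinib exposure condition, although only apatinib is escalated, so some under-exposed subjects count as toxicity-free

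*Protocol*

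**What the plan says.** Protocol 3.1 sets up three Stage I groups that differ only in daily apatinib (250, 375 or 500 mg); SHR-1210 is 200 mg every two weeks in all of them. "Ten to twelve subjects will be enrolled in each dose group", and the first 28-day cycle is the observation period. The decision rule is: "A dose will be considered tolerable if the proportion of subjects with clinically significant toxicity is < 0.33".

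Protocol 3.1.2 calls a subject's evaluation incomplete when "the dose of SHR-1210 is < 90% of the prescribed dose due to non-clinically significant toxicity (such as injection reactions". The consequence is that "Subjects who do not complete the tolerability evaluation will not be included in the overall number of subjects undergoing tolerability evaluations". Each group needs at least 10 subjects. Under an exemption, a group passes and closes to enrolment once seven or more subjects are free of clinically significant toxicity.

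The DLT analysis set in SAP 5.1.1 takes in "Subjects enrolled in Stage I who have developed DLT during the tolerability observation period (four weeks) or have completed the tolerability observation period" and removes "Subjects with SHR-1210 dose < 90% of the prescribed dose due to non-clinically significant toxicity (such as injection reaction" during that period. SAP 5.4.2 tabulates clinically significant toxicity by dose group on this set.

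Apatinib intake enters in one place only. Item 5 of the toxicity definition in protocol 3.1.1 counts as an event: "Apatinib interruption for > 7 days due to relevant toxicity".

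**The concern.** The question in Stage I is how much apatinib can be added to a fixed SHR-1210 dose. A subject informs that question only if the assigned apatinib was largely taken, but the evaluability rule never asks.

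SHR-1210 exposure is not a substitute. It is infused in clinic on Days 1 and 15, while apatinib is taken daily at home. The dose modification table in protocol 6.4 also has several rows where apatinib is interrupted and SHR-1210 is not. A subject can receive both infusions, miss a substantial part of the apatinib, have no qualifying toxicity, and be counted as tolerating a dose that was not taken.

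The protocol recognises the problem elsewhere. In the expanded PK study (3.2.1), an adverse-event-related apatinib interruption in the last week of Cycle 1 means the subject has not completed the PK study and must be replaced. The tolerability part has no counterpart. At stake is the primary Stage I result, the proportion with clinically significant toxicity at each apatinib dose.

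**Working it through.** **1. The plan's own rule.** Solve x/n < 0.33 for the group sizes allowed:

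- n = 10: 3/10 = 0.300 passes and 4/10 = 0.400 does not, so 7 toxicity-free subjects are needed. This matches the exemption.
- n = 11: 3/11 = 0.273 passes; 4/11 = 0.364 does not.
- n = 12: 3/12 = 0.250 passes; 4/12 = 0.333 does not.

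The limit is three toxic subjects throughout. (At n = 11 or 12 the exemption would admit 4/11 = 0.364 or 5/12 = 0.417, against the 0.33 rule. That is a separate matter to reconcile. The work below uses n = 10, where the two rules coincide.)

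**2. Which apatinib shortfalls escape.**

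- Toxicity-related interruption of more than 7 days: an event under item 5, so no gap.
- Toxicity-related interruption of 7 days or less: not an event under item 5; at least 28 − 7 = 21 of 28 days (75%) can remain. These subjects were exposed, so this is the weaker part of the concern.
- Reduced or intermittent apatinib under protocol 6.4: not in itself an event.
- Doses missed for reasons other than toxicity: no limit is stated.

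**3. Direction.** With x events among n adequately exposed subjects, one added under-exposed subject without toxicity gives x/(n + 1), which is never above x/n. An under-exposed subject with toxicity is an event under either definition. The effect therefore runs one way.

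**4. Size, as an illustration.** Count 10 subjects, k of them under-exposed. Let the true toxicity rate be p in exposed subjects and f × p in under-exposed subjects, with f = 0 (zero risk) or 0.5 (half risk). Then P(pass) = P(X + Y ≤ 3), with X ~ Bin(10 − k, p) and Y ~ Bin(k, f × p). At p = 0.40:

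- k = 0: P(Bin(10, 0.40) ≤ 3) = 0.382.
- k = 1, zero risk: P(Bin(9, 0.40) ≤ 3) = 0.483.
- k = 1, half risk: 0.8 × 0.4826 + 0.2 × 0.2318 = 0.432, where 0.2318 = P(Bin(9, 0.40) ≤ 2).
- k = 2, zero risk: P(Bin(8, 0.40) ≤ 3) = 0.0168 + 0.0896 + 0.2090 + 0.2787 = 0.594.
- k = 2, half risk: 0.64 × 0.594 + 0.32 × (0.0168 + 0.0896 + 0.2090) + 0.04 × (0.0168 + 0.0896) = 0.485.

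Other true rates (ranges run from half risk to zero risk):

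| p | k = 0 | k = 1 | k = 2 |
|---|---|---|---|
| 0.25 | 0.776 | 0.805–0.834 | 0.833–0.886 |
| 0.33 | 0.568 | 0.613–0.658 | 0.658–0.748 |
| 0.40 | 0.382 | 0.432–0.483 | 0.485–0.594 |
| 0.50 | 0.172 | 0.213–0.254 | 0.261–0.363 |

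Every cell has 10 counted subjects, so the comparison respects the minimum group size.

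**The case against.** The documents are not empty on this point. Protocol 3.1 describes the observation period as 28 days of uninterrupted treatment, and the SAP requires a subject without DLT to have completed it. One could read a subject who missed much of the apatinib as not having completed it. Poor compliance is a ground for discontinuation in protocol 5.3.1, and item 5 makes long toxicity-related interruptions events. All of this narrows the gap. It does not close it, because neither document ties completion to apatinib doses taken, and the SAP states an exposure exclusion for SHR-1210 alone.

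The SHR-1210 clause is itself limited to shortfalls caused by toxicity that is not clinically significant. It is just as silent on infusions missed for supply, choice or compliance. A remedy for apatinib alone would leave that hole open. This stands, and the fix covers both drugs.

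SAP 5.4.1 summarises apatinib interruptions, modifications and relative dose intensity. But SAP Table 2 derives intensity from first to last dose, not over Cycle 1, and nothing links it to the DLT set.

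A reader might infer that 3 toxic subjects among 9 properly exposed would be a failed dose (0.333) rescued by a tenth, under-exposed subject (0.30). The protocol does not support that. With 9 subjects the group is incomplete and another must be enrolled; at a true rate of 0.40, that subject would be free of toxicity 60% of the time and the group would pass at 3/10.

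**Conclusion.** The gap holds in both documents. Subjects without clinically significant toxicity who missed a substantial part of the apatinib for reasons outside item 5 count as toxicity-free, towards both the 0.33 rule and the exemption. The effect can only favour calling a dose tolerable.

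Its size is unknown. The illustration rests on an assumed true toxicity rate, an assumed number of under-exposed subjects (one or two in ten) and an assumed risk in them (zero to half); none of these is in the documents. At a true rate of 0.40, the chance of passing rises by about 5 to 10 percentage points with one such subject and 10 to 21 with two. The upper ends need zero risk, which does not suit someone who took most of the doses, so they are bounds and not estimates.

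A reader might also infer that a dose was wrongly passed or the Stage II dose wrongly chosen. The documents do not support this. Protocol 3.1 already selects 250 mg, the lowest of the three, after Stage I results and discussion between sponsor and investigators, and the SAP's analysis groups cover only 250 and 375 mg. What can still change is the reported tolerability conclusion. The point is a worthwhile, inexpensive improvement.

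**What to change.** SAP section 2 says the SAP is finalised before database lock, so the change can still be made:

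- In the DLT analysis set (SAP 5.1.1), define completion of the observation period by Cycle 1 exposure to both drugs, whatever the reason for a shortfall.
- Let the sponsor fix the minimum apatinib intake in advance, without reference to who had toxicity. Treating fewer than 21 of 28 planned doses as not evaluable is one option that mirrors the 7 days in item 5. It defines an analysis set, not a dosing rule.
- Keep every subject with clinically significant toxicity evaluable, whatever the exposure.
- In the SAP 5.4.2 table, give the toxicity proportion per dose group under the existing and the exposure-based definitions. List the subjects who differ, with their Cycle 1 apatinib intake and the reason for the shortfall.

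The reason matters. A 7-day interruption for lesser toxicity followed by 21 days of five-on, two-off dosing gives 21 × 5/7 = 15 doses. Such a subject would leave the exposure-based set although the modification itself says something about tolerability.

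The data exist: note 23 to the schedule of activities requires remaining tablets to be returned and checked on Day 1 of Cycle 2. The cost is a sentence or two in the SAP and one more column in a table. The downside is that a group may show fewer than 10 evaluable subjects under the new definition, which the side-by-side report makes plain. If nobody was under-exposed, the columns agree and the tolerability statement is stronger.

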Study Design	
Study design of Stage I:
 
A multi-arm, multi-center, open-label clinical study
 
Inclusion criteria: Patients with advanced NSCLC who have failed standard treatment.
 
Three dose groups, i.e., 250 mg apatinib, oral, q.d. + 200 mg SHR-1210, IV, q2W, 375 mg apatinib, oral, q.d. + 200 mg SHR-1210, IV, q2W, and 500 mg apatinib, oral, q.d. + 200 mg SHR-1210, IV, q2W are set up to explore the tolerability of the combination therapy.
 
Ten to twelve subjects will be enrolled in each dose group (to make sure that at least 10 subjects will complete the tolerability evaluation), and the first cycle (28 days) of continuous treatment will be used as the observation period for tolerability. A dose will be considered tolerable if the proportion of subjects with clinically significant toxicities is < 0.33.
 
After completing the tolerability observation period, subjects will continue the treatment until occurrence of any event that meets the criteria for discontinuation.
 
After completing the tolerability observation period, the study will enter Stage II for further observation of efficacy and safety.
 
After the completion of the observation period for tolerability, 10 to 12 subjects will be enrolled in each dose group for an expanded pharmacokinetic study. In cycle 1 of the expanded PK study, one dose of SHR-1210 will be administered on D1 followed by PK blood sampling. Then, apatinib will be started on D22 after the completion of PK blood sampling, while another PK blood sampling will be carried out on D28. Starting from D1 in cycle 2, SHR-1210 will be administered once every 14 days, while apatinib will be administered orally every day. PK blood sampling will be carried out on D1 of cycle 2 after the administration of SHR-1210 and on D28 after the administration of apatinib. After the blood sampling is completed, the subjects will continue to receive the study treatment until an event meeting the criteria of study termination occurs.
 
Design of Stage II:
 
A single-arm/double-arm, multicenter, open-label clinical study
 
According to the tolerable doses for combination therapy determined in Stage I, apatinib 250 mg, q.d. oral + SHR-1210 200 mg, IV, q2W are selected, and patients with advanced non-small cell lung cancer who failed first-line chemotherapy or patients with non-squamous non-small cell lung cancer with a high tumor mutation burden (TMB) confirmed by the central laboratory are planned to be enrolled. According to the molecular and pathological classifications, the subjects are divided into:
 
Cohort 1. Non-squamous, non-small cell lung cancer with wild-type EGFR and ALK;
 
Cohort 2. Non-small cell lung cancer with EGFR mutation or ALK fusion gene rearrangement. The subjects harboring sensitive EGFR mutations and ALK fusion gene rearrangement must have failed the treatment of at least one EGFR inhibitor or ALK inhibitor;
 
Cohort 3. Non-central squamous cell lung cancer;
 
Cohort 4. Non-squamous and non-small cell lung cancer with wild-type EGFR and ALK and with $\text{bTMB} \geq 1.54 \text{ muts/Mb}$ or $\text{tTMB} > 10 \text{ muts/Mb}$ confirmed by central laboratory.

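### The tolerability exemption in protocol 3.1.2 has no cap on toxicities, so at 11 or 12 evaluable subjects it accepts doses that the < 0.33 criterion rejects

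*Protocol*

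**What the plan says.** The main rule is in protocol 3.1: "A dose will be considered tolerable if the proportion of subjects with clinically significant toxicity is < 0.33". The synopsis and SAP 2.1 state the same rule. Each dose group enrols 10 to 12 subjects, and the reason given for the range is "to make sure that at least 10 subjects will complete the tolerability evaluation". The first three subjects enter at least 14 days apart; after that, "subsequent subjects can be enrolled at the same time".

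Protocol 3.1.2 removes subjects with incomplete evaluation from the denominator and adds that "each dose group is required to have ≥ 10 subjects for the tolerability observation". The exemption comes next: "If ≥ 7 subjects in a dose group do not develop clinically significant toxicity during the tolerability observation period", then "the dose group is considered to be tolerable and no new subjects will be enrolled into this dose group".

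The verdict controls escalation, since "the tolerability observation of a latter dose group can only be carried out after the previous dose group is confirmed to be tolerable". Under protocol 3.1 it also controls whether the PK expansion opens at that dose. The exemption does not appear in the SAP.

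**The concern.** The criterion is a proportion. The exemption is a count of toxicity-free subjects that says nothing about how many others had toxicity. A fixed count of 7 corresponds to a fixed proportion at only one group size. Once a group can be larger than that size, the same data can be tolerable under one rule and not tolerable under the other, and the exemption is then the more permissive of the two. At stake are the tolerability verdict for each dose, which belongs to the primary objective of Stage I, and the steps that follow from it: escalation and the PK expansion.

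**Working it through.** **Inputs.** Criterion: x/n < 0.33, strict, where x is the number with clinically significant toxicity and n the number evaluable (protocol 3.1, 3.1.2). Group size: 10 to 12 enrolled, at least 10 evaluable. Exemption: n − x ≥ 7 (protocol 3.1.2).

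**Where the 7 comes from.** At n = 10 the largest x with x/10 < 0.33 is 3, so at least 10 − 3 = 7 subjects must be free of toxicity. The protocol's figure is the criterion solved at n = 10.

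**The two rules at each size.** The exemption allows up to n − 7 toxicities.

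| n evaluable | Most toxicities under < 0.33 | Most under exemption | Worst proportion under exemption |
|---|---|---|---|
| 7 | 2 | 0 | 0/7 = 0 |
| 8 | 2 | 1 | 1/8 = 0.125 |
| 9 | 2 | 2 | 2/9 = 0.222 |
| 10 | 3 | 3 | 3/10 = 0.300 |
| 11 | 3 | 4 | 4/11 = 0.364 |
| 12 | 3 | 5 | 5/12 = 0.417 |

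At 7 or 8 the exemption is stricter. At 9 and 10 the rules coincide. At 11 it accepts 4/11, and at 12 it accepts 4/12 = 0.333 and 5/12, where the criterion stops at 3. Reading the limit as exactly 1/3 changes nothing, because 4/12 is not below 1/3.

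**Can it be reached?** With parallel entry after the third subject, 11 or 12 can be on treatment before the seventh toxicity-free result is known. With one-by-one entry, it needs an eleventh evaluable subject after 4/10.

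**How often the rules disagree.** The documents give no true toxicity rate, so rates p are assumed and outcomes are taken as independent. With all subjects observed together:

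- n = 11: C(11,4) p⁴(1−p)⁷
- n = 12: C(12,4) p⁴(1−p)⁸ + C(12,5) p⁵(1−p)⁷

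At p = 0.40, n = 11: 330 × 0.0256 × 0.02799 = 0.2365. At p = 0.40, n = 12: 0.2128 + 0.2270 = 0.4399 (from unrounded terms).

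| Assumed p | n = 10 | n = 11 | n = 12 |
|---|---|---|---|
| 0.20 | 0 | 0.1107 | 0.1860 |
| 0.30 | 0 | 0.2201 | 0.3896 |
| 0.40 | 0 | 0.2365 | 0.4399 |
| 0.50 | 0 | 0.1611 | 0.3142 |
| 0.60 | 0 | 0.0701 | 0.1429 |

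**Chance of being called tolerable at p = 0.40.** Criterion P(X ≤ 3): 0.3823 (n = 10), 0.2963 (11), 0.2253 (12). Exemption P(X ≤ n − 7): 0.3823, 0.5328, 0.6652.

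**One-by-one entry.** Disagreement then requires the fourth toxicity to come before the seventh toxicity-free subject, with enrolment continuing. At p = 0.40 this gives C(10,4) p⁴(1−p)⁷ = 0.1505 by n = 11. Adding C(11,5) p⁵(1−p)⁷ = 0.1324 gives 0.2829 by n = 12.

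**The case against.** The strongest reply is that the exemption was never meant to work above 10. It follows directly on the requirement for at least 10 subjects and is most naturally read as waiving that minimum: once 7 are free, a group of 10 can have at most 3/10. The stated purpose of subjects 11 and 12 is to replace non-evaluable ones. Under that reading there is no conflict, and one-by-one entry would hardly go on after 4/10 had already failed. This is probably the intent, and it limits how far the point reaches. It does not remove it, because 3.1.2 neither restricts the exemption to 10 evaluable subjects nor says that it waives only the minimum.

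Two further complaints might be inferred, and the documents support neither. First, a reader might say that the plan lacks a count at which a dose is intolerable. That count follows from the criterion: 4/10, 4/11 and 4/12 all fail < 0.33, and protocol 3.1 already blocks escalation unless the dose is confirmed tolerable. Second, a reader might say that SAP 5.4.2 leaves open which rule decides. The SAP contains only the < 0.33 rule (2.1). It already reports the size of the DLT analysis set (5.2.1) and the frequency and percentage of clinically significant toxicity by dose group (5.4.2), so a reader of the report can check the criterion directly.

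**Conclusion.** The point holds in a narrow form. As written, the exemption contradicts the < 0.33 criterion at 11 or 12 evaluable subjects and at no smaller size. Where it applies the difference is large: at an assumed true rate of 0.40, observed together, 53% against 30% called tolerable at 11 and 67% against 23% at 12. These figures rest on the literal reading, on assumed toxicity rates, and on a group actually having 11 or 12 evaluable subjects.

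It would be tempting to conclude that an overly toxic dose was carried forward. The documents do not support that. Protocol 3.1 (Stage II) records 250 mg, the lowest apatinib dose, as already selected from the Stage I results after discussion between the sponsor and the principal investigators. The SAP's groups cover only 250 mg and 375 mg (section 5). Neither document states how many subjects per dose were evaluable; if no group exceeded 10, no verdict changes. What remains is the verdict reported for each Stage I dose and the rule for any dose group still to be judged. The repair is cheap and worth making.

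**What to change.** In the protocol 3.1.2 exemption, after the condition on 7 toxicity-free subjects, add: 'and no more than 3 evaluable subjects have clinically significant toxicity, including any still under observation'. Subjects still under observation are to be counted as possible toxicities, so that a verdict reached under parallel entry cannot be overturned by a pending result. The exemption then does no more than waive the minimum of 10. It agrees with the criterion at every planned size, since 3/10 = 0.300, 3/11 = 0.273 and 3/12 = 0.250 pass and a fourth toxicity fails.

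In SAP 5.4.2 add: 'The tolerability verdict for each dose group follows the < 0.33 criterion in the DLT analysis set; if the protocol 3.1.2 exemption gave a different verdict for a completed group, both are shown.' The second clause prevents a dose already judged from being relabelled without notice.

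Cost: the protocol wording needs ethics approval (protocol 11.1 and 11.2). The SAP sentence can be added before database lock. Some groups of 11 or 12 that the literal exemption accepts become not tolerable, including some at acceptable true rates: if observed together, 11% and 19% at a true rate of 0.20, and 22% and 39% at 0.30. At 10 evaluable subjects nothing changes.
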